Analysis of primary outcome. For our PHQ-9 primary outcome, we will test whether there are differences in score trajectories across time between arms with two-level hierarchical linear models (HLMs) in a growth curve framework. The first level of the model will include time as a predictor, modeling within-person variation. The second level will include a dummy variable for arm (e.g., 1=TAU+BLT+AP or TAU+BLT, 0=TAU) as the predictor variable for both the random effects of the intercept and slope for time. A significant coefficient for arm on the time slope would indicate that there are different trajectories across time for BLT arms versus TAU.

We will probe any significant arm x time interactions by graphing the simple-effects equations to determine whether the observed pattern is consistent with hypotheses.

Moderation and mediation. In addition to primary outcome analyses we will conduct exploratory analyses of moderation using variables identified through previous research and clinical expertise, specifically indication of pharmacotherapy use (1=yes, 0=no), age (continuous), gender (1=female, 0=male), race and ethnicity (1=racial/ethnic minority, 0=non-Hispanic white), baseline PHQ-9 (1=clinically elevated, 0=below clinical range), and EHR indication of mental health comorbidities such as eating disorders, anxiety (1=comorbidity, 0=no comorbidity). Moderation will be indicated by a significant time x arm x moderator interaction in HLM.

We will conduct exploratory analyses of the BLT mediation pathway as the extent to which the relation between BLT and outcomes is mediated by changes in participants' 1) sleep (SASS-Y and actigraphy, and PSQI subjective sleep quality), 2) total physical activity, and 3) circadian timing and chronotype. For example, to evaluate the mediating effect of PSQI sleep quality we will regress post-acute treatment PSQI on baseline PSQI and a randomization condition indicator; and we will regress follow-up PHQ-9 at post-acute treatment PSQI and a randomization condition indicator. Using the product coefficients mediation approach, we will use the resulting regression coefficients and standard errors (SEs) to estimate the indirect effect. Because SEs of the products of regression coefficients are not normal, we will use bias-corrected bootstrapping to estimate the SEs for the indirect effect. We will use a similar approach for the MI pathway to test the mediating effect of participants' increased readiness to change on BLT adherence.

Analysis of secondary outcomes. Continuous measures over time will be modeled with HLM methods described above. Health service use can be categorized into binary (e.g., met threshold for medication possession ratio, had > 1 hospitalization) and count outcomes (e.g., N of ED visits, primary care visits). Binary outcomes will be modeled with multivariable logistic regression, and the coefficient of study arm membership (e.g, 0=TAU, 1=TAU+BLT+AP & TAU+BLT) is the coefficient of primary interest. Count outcomes are modeled with either multivariable Poisson or negative binomial regression depending on which yields optional fit.

BLT process outcomes. To examine the effects of adherence and MI elements, we will contrast Arms 2 vs. 3 across months 2, 4, and 6, comparing: (a) % cumulative light box purchase; (b) % cumulative compensation for light box purchase; and (c) mean EMA-adherence (aka, dose). We will conduct these analyses using methods similar to those for secondary outcomes; however, the analysis sample will be restricted to Arms 2 and 3. We will describe similar metrics in the TAU condition (Arm 1).

Economic analysis. The future full trial will conduct a cost-effectiveness analysis (CEA) of the BLT intervention relative to TAU to inform the merits and costs of implementing such a program. In this pilot we will conduct both the relevant data collection and the economic analyses to prepare for this. Two major CEA cost components include 1) TAU costs related underlie all study arms, and 2) costs of the BLT intervention, including the equipment but also phone coach staff time. This pilot study provides the opportunity for our research team to hone the data collection process and measurement of these cost components, building on our several previous economic analyses conducted in concert with our mental health RCTs. While this pilot is underpowered to detect significant difference in costs between study conditions, we will be able to richly describe and categorize TAU services underlying each condition. In addition, [name] will lead efforts to estimate the total cost of the intervention by developing a data collection tool for phone coaches and research staff to track time used to the deliver the interventions. He will also periodically meet with those who are providing data to assess whether the tools are meeting their needs and if the data are truly capturing the resource intensity needed to deliver the protocol. This tool will be submitted in a subsequent modification.

Power analysis, sample size. The R34 pilot funding cap limits us to a feasibility sample that is insufficient for an adequately powered test of the hypothesis. Nonetheless, we provide an estimate of the statistical power obtained from this sample of a minimum of 90 participants (up to 100 pts if recruitment success

allows). Meta-analyses suggest an overall effect size for BLT of $d=0.84$. We conservatively estimate the effect size likely to be obtained in this pilot trial as lower than reported in meta-analyses because this is a real-world effectiveness population; even with Arm 3 adherence promotion BLT adherence is likely to be lower than in efficacy trials, leading to lower clinical benefit. Assuming a retained sample size of $N=81$ at the final 6-month assessment, we conducted power analysis for the HLM of the primary outcome (using SAS version 9.4) to determine the minimum detectable effect size. At a two-tailed alpha level of 0.05 and conservatively assuming an autocorrelation of 0.70, we would have 80% power to detect a Cohen's d for the time by arm effect as small as 0.39 for the contrast between active intervention arms (Arms 2 and 3) and TAU, and as small as 0.55 for contrasts between individual arms; both estimates are medium effects. This pilot study is not powered to evaluate mediation, but we will conduct mediation analyses as if this were the full-powered R01 confirmatory trial to test feasibility of the analytic methods and to provide informative estimates of potential mediators. We estimate that we will have 80% power using a 95% bias-corrected confidence interval to identify effect sizes of 0.43 or larger for the pathways between randomization status to mediator, and mediator to outcome (BLT adherence for MI pathway, and PHQ-9 for BLT pathway); and we will be able to identify direct and indirect effects of 0.19 or larger, which correspond to a small-medium effect.

Use of pilot results to estimate power for the future full trial. Regardless of the between-condition effect size that we observe in this pilot, we will heed the cautions that have been raised about using pilot study results to estimate effect for full trial power/sample calculations. We will consider between-condition effect size (ES) results highly tentative given the small pilot sample and will use it only with wide confidence intervals when employing it to estimate power for the future full pragmatic trial. For example, if we obtain an effect size of $d=0.45$, we will generate a power/sample size matrix with estimated effects of 0.35, 0.40, 0.45, 0.50—all ranging around the observed effect from this pilot, but trending to somewhat smaller and more conservative effects.

b. Sharing of Results with Subjects

Immediate, individual level results will not be shared with participants. However, approximately 6 months after the study end we will send a brief summary of the results to participants via email and/or US post.

c. Data and/or Specimen Banking

Data collected for this research will not be used for future unspecific research. No specimens are collected in this study.

7. Privacy, Confidentiality and Data Security

Additional Information about Sensitive Data

As described previously, mental health diagnoses and/or records will be collected (e.g., prescription dispensing data and health care utilization). These data are necessary to identify potentially eligible participants in the recruitment phase and to examine possible moderators of effects during analysis.

Describe the plan for storage of data and/or specimens.

Data collected for all participants will be kept strictly confidential, except as may be required in the case of a psychiatric or medical crisis (reporting abuse, imminent danger to self or others). All research files

are kept on a secure server that uses multiple layers of data protection, and all research personnel sign a confidentiality agreement and receive human subjects protection training. These data are only used for the purpose of recruitment and for contacting study participants during the course of the study.

Data from participants who do not qualify for participation will be collected, including the reasons why participants did not qualify, and basic demographics from the EHR that are associated with the case-finding program (e.g., age, gender, gender minority status, race, ethnicity). This data will be used to enhance recruitment efforts in planned randomized control trial proposals, by permitting us to understand whether our study and/or recruitment methods may be less often acceptable to certain demographic groups. The data will be retained no longer than three years.

A unique study identifier will be assigned to each study participant and used to code the data.

Paper Data: We do not plan to utilize any hard copies of data. However, if it is necessary to collect hard copies (e.g., REDCap is unavailable), hard copies of data will be kept in a locked office at KP CHR to which only research staff has access. Hard copies of paper data will be stored at any location where staff are working remotely. Data for all participants will be kept strictly confidential, except as mandated by law. All research files are kept in locked file cabinets or in a locked file room.

Collection of data from subjects electronically

Electronic data will either be (a) stored on the study file service, which is accessible only to study staff who have been given access by the project manager or the principal investigator, or (b) stored in REDCap. Assessment and intervention data will be collected via REDCap. An email containing a unique survey link will be sent to participants or data will be directly entered into REDCap by study assessment staff. Within REDCap data collection forms, participants will be identified by a study ID only.

Recordings: Recordings of intervention contacts with participants will be stored on a secure file server at CHR, using the study ID for identification. These recordings will be used for training and quality assurance purposes only. A select sample of the recordings will be securely transferred to our research collaborator, [name], via the SFT site for quality assurance purposes. [name] will access the SFT website through a uniquely assigned account and download the files to a secure location on their network.

Destruction of Identifiers: Once the study is completed, identifiable information will be removed from the study tracking system and stored in the CHR secure electronic data storage system until such time that the PI no longer needs the data. At that time, the data will be professionally erased following standard procedures in place at that time. Identifiable information in paper form will be stored in the secure off site storage area until the PI no longer needs the data at which time it will be returned to the CHR and sent to be shredded.

Does this study involve the disclosure of PHI to a collaborator?

[name]. A select sample of phone coaching call recordings will be securely transferred to our research collaborator, [name], via Secure File Transfer for quality assurance purposes. [name] will access the SFT website through a uniquely assigned account and download the files to a secure location on their network. While the recording files will be labeled with study ID and study staff will not solicit PHI, it is always possible that a participant will share a name or other unique identifier during a recorded phone coaching call.

National Database for Autism Research (NDAR). This study is subject to NIH policies on data banking with NDAR. We will submit data on study participants to NDAR via the National Institute of Mental Health Data Archive system. Data will be de-identified prior to upload to the NDA. However, there remains the possibility of deductive disclosure of participants with unusual characteristics.

Data Commitments (data and specimen sharing)
FROM KPNW

Recipient and Description of Materials	Identifiers* (note w/an X)	Health Information** (note w/an X)	HIPAA Documentation (see policy NWRC.PRIV.04)
[name] Phone coaching call recordings labeled with study ID will be shared via SFT. Study staff will not solicit PHI during recordings, but it is possible that a participant will share a name or other unique identifier during a recording.	 Fully Identifiable  Limited Data Set  De-Identified  Aggregate	 Yes  No	 Signed Authorization  Waiver of Authorization  Limited Data Set only (DUA Required)  De-Identified or Aggregate Data  N/A, No Health Information
National Database for Autism Research (NDAR) We will share de-identified participant data with the National Institute of Mental Health Data Archive (NDA) as required by the NOA.	 Fully Identifiable  Limited Data Set  De-Identified  Aggregate	 Yes  No	 Signed Authorization  Waiver of Authorization  Limited Data Set only (DUA Required)  De-Identified or Aggregate Data  N/A, No Health Information

8. Provisions to Monitor Data to Ensure the Safety of Subjects

[name] will assume responsibility for and oversee patient safety on the overall project. Drs. [name] and [name] will liaise with a data safety monitoring board (DSMB), which will have overall review responsibility for patient safety and serve as a reporting body to the NIMH and study IRB. The DSMB will consist of 3 TBN members: a community mental health advocate, a biostatistician, and another clinical or research mental health expert.

The DSMB will conduct twice-yearly reviews to determine whether patient safety has been adequately safeguarded. The DSMB members, in consultation with [name], are empowered to take whatever immediate action is necessary to safeguard the welfare of individual patients. The DSMB group will also examine adverse events (AEs) annually, and serious adverse events (SAEs) as they occur (see reporting times below). Safety information will be collected at each assessment timepoint as described previously in section 6 under "Monitoring for Safety".

[name] will generate quarterly interim reports for the DSMB as well as summary 6-month reports. These interim analyses will be conducted for safety outcomes (suicidal behavior, other crises, study terminations, all AEs, SAEs, other events) and data quality indicators (recruitment, retention, instrument reliability, intervention fidelity), but not routinely for clinical effectiveness or economic outcomes. Study conditions will be masked (e.g., Red, Green, Blue arms) in these safety and data quality reports but the DSMB can request unblinding at its discretion should a safety or data quality concern arise.

The study team will notify the IRB and the DSMB (and as required, the NIMH Project Officer) of any clinically significant new emergent issues detected in this study, even if seemingly unrelated to the study, BLT or procedures (e.g., new diagnosis of cancer). We will follow KPNW IRB reporting dates for DSMB notification. In many cases, because the study does not routinely assess participants for new emergent issues that are not anticipated as a possible risk (see list of expected clinical issues in section 6 under "Monitoring for Safety"), these incidental diagnoses/conditions will be detected either through spontaneous patient report or review of the electronic health record (EHR). Given that all participants are members of the Kaiser Permanente health organization, in the case of new EHR-recorded diagnoses/conditions this means that the usual care health providers (primary care providers, mental health and other specialists) will already know about and will be addressing these conditions/diagnoses.

Given the enrolled population will have been pre-identified by virtue of EHR depression clinical diagnosis or elevated PHQ-9, none of the clinical events summarized previously (worsening depression, suicide/self-harm, new comorbidity, Bipolar Disorder) are considered 'unexpected.' In other words, they are not unusual given the high comorbidity of depression with other mental disorders generally. Suicide, self-harm, anxiety, substance misuse and BD are particularly possible given the case-selection for active depression disorder and/or symptomatology. In this study, the most likely anticipated event possibly related to research would be the precipitation of BD and any variant on exposure to BLT. We will make appropriate clinical referrals to emergency or non-emergency services, and/or communicate with TAU providers as warranted – and as summarized previously.

9. Risks and Benefits

a. Risks to Subjects

The assessments and treatments in this study pose no greater risk than standard treatment or therapy, or clinical interviews. These risks include:

1. The potential for an unintended breach of confidentiality. We will be in touch with participants by email and text message to schedule study events or to remind them about surveys. Any confidential information sent through the Internet or by text message has a small risk of being read by someone other than the person it was sent to. As described in the data handling section above, we will store all information in locked cabinets, on password protected servers, or within REDCap (a HIPAA-compliant, web-based application for data capture).
2. The possibility of distress in association with addressing emotional difficulties during the completion of surveys or study activities. Participants are free to refuse to answer any questions and will be reminded of this prior to addressing sensitive subjects.
3. Engaging in bright light therapy may have risks for individuals with vulnerability to phototoxicity, photosensitive skin, or who are taking a photosensitizing medication or herb. Our EHR case-finding program will exclude patients with active EHR diagnoses and prescriptions representing any of the few contraindications for BLT. We will also ask about these diagnoses and conditions during the screening survey to further exclude those with these potential contraindications.
4. There is a small risk of manic activation from BLT light exposure. This risk is inherent in the general population and could occur whether or not individuals were enrolled in the study. Our EHR case-finding program will exclude patients with any variation of bipolar disorder recorded in the EHR. We will also screen for emerging symptoms of mania during the screening survey and follow-ups. We will inform the TAU providers of our participants that their patients are participating in this study, which may involve self-administration of BLT. If study staff suspects a participant is in danger or unsafe, they will immediately report this to a licensed study team member and discuss possible strategies for responding (see DSMP section for more details).

Some participants may become pregnant during the study. However, nothing in the study procedures or interventions is expected to have any adverse impact on the mother or child.

b. Potential Benefits to Subjects

The study treatment participants may utilize as a result of participating in this study may help improve their well-being and functioning and reduce mental health problems. Additionally, participants often feel good that participating in research may help other people.

10. Economic Burden to Subjects

There are no costs to participants for study assessments or study phone coaching activities. However, participants may incur the following costs during participation:

- Usual care underlies all three arms of the study, and some of that usual care may be directed at depression. Participants may incur costs for usual care; e.g., co-pays; paying for treatment, therapies, or other interventions. However, the delivery of these usual care services will be at the discretion of the KP providers, or community providers for usual care services participants may receive outside of KP.
- Participants in study arms 2 and 3 will be encouraged, but not required, to purchase a light box with an estimated cost of \$70 to \$200 depending on the model. All of these participants will be provided with written information about obtaining compensation (up to \$80 in Fred Meyer gift

cards) for this purchase through the study. In Arm 3, a study coach will guide participants to obtain compensation. Participants will be responsible for any purchase price greater than \$80. The study light box compensation process is modeled to simulate the KP durable medical equipment (DME) benefit, which does not currently cover LBs for non-SAD depression. Preliminary conversations with the DME decision group seem to indicate willingness to cover LBs for non-SAD depression when a published meta-analysis determines that there is sufficient evidence of LB benefit for non-SAD depression. While there are individual studies showing LB benefit for non-SAD depression, this evidence does not quite meet the threshold for changing the DME benefit.

Participants will be informed of these potential costs in the consent information form and during the recruitment call with our staff.

11. Compensation to Participants

Participants will be provided with Amazon gift certificate incentives for participating in each assessment (\$25 for baseline, \$25 for 2-month follow up, \$30 for 4-month follow up, \$40 for 6-month follow up). Participants are compensated for completing each assessment, even if the participant chooses to not finish all portions of the surveys. Participants who complete the qualitative interview will be provided with a \$20 Amazon gift certificate. Participants will be notified of the compensation details in the consent information sheet and during the recruitment call with our staff.

12. Resources Available

Not applicable.

13. Additional Approvals

Not applicable.

14. Drugs or Devices**a. Drug Studies**

Not applicable.

b. Device Studies:

Not applicable.

15. Multi-Site Research

N/A

16. Community-Based Participatory Research

N/A

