- Active EHR diagnoses and prescriptions representing any of the following contraindications for BLT: Conditions that might render skin or eyes more vulnerable to phototoxicity (e.g., ophthalmic disorders such as cataract, macular degeneration, glaucoma, retinitis pigmentosa; disorders affecting the retina such as retinopathy, diabetes, herpes); or photosensitive skin; or if they are taking a photosensitizing medication or herb (e.g., St. John's wort or a psoralen).
- EHR-recorded diagnoses of bipolar disorder I or II.

Screening inclusion criteria:

- Elevated PHQ-9 (score of 10 or higher);
- Able and willing to conduct study assessments and phone coaching in English;
- Phone and internet access.

Screening exclusion criteria:

- Participation barriers (e.g., terminal end-stage cancer, moving out of the region, no locator information);

- Contraindicated diagnoses or medications (see EHR exclusion criteria above) in case these are known to patients but are not EHR-recorded (e.g., if they were diagnosed with a contraindicated condition before becoming a KP member and have not yet sought care for it);
- Contraindicated diagnoses or medications (see EHR exclusion criteria) newly reported that were not captured in the EHR;
- Emergent bipolar, manic, mixed symptoms that may not have been formally diagnosed yet (e.g., significant mood swings, excessive increases in energy, dramatically less need for sleep).

In the event of a screen failure, or when a potential participant is contacted but declines participation, minimal demographic data collected (such as age, sex, race, ethnicity), and reason for declining will be retained for review. This data may help inform future study design.

c. Vulnerable Populations

Vulnerable Populations (VPs)	Include/Exclude	Rationale
Pregnant women	Include	Pregnancy has no known vulnerabilities for BLT. Further, BLT may be a valuable alternative treatment for pregnant women who might be hesitant to take antidepressants.
Children	Exclude	N/A
Neonates of uncertain viability or nonviable neonates	Exclude	N/A
Prisoners	Exclude	N/A

d. Setting

This study will be conducted by study staff at Center for Health Research (CHR), among the KPNW adult membership. Participants will be able to conduct all study activities from home.

e. Recruitment Methods

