EHR Identification of Potential Recruitment Pool. We will run an EHR case-finding program as needed for the projected 16-month recruitment period to generate an initial outreach list of potentially eligible individuals. After each recruitment list is generated, we will send a secure EHR message to each individual's primary care provider (PCP) and mental health specialist (e.g., psychiatrist) if applicable. In this message, we will state our intent to reach out to the patient unless we hear from the provider within three business days that it would be unwarranted (e.g., due to more acute condition for which other health care should be primary).

Once an individual has been identified once by this EHR search program, they will be excluded from subsequent runs of the program to avoid multiple waves of contact.

Recruitment Mailing, Emailing, Online Screening, and Calls. For patients not opted out by clinician(s), we will mail/email a recruitment packet containing the recruitment letter, recruitment flyer, and a copy of the consent information sheet. Interested patients have the option to complete the screening survey online. For those who screen eligible online, study staff will follow up by phone to obtain verbal informed consent as described in Section F. Patients also have the option to opt out online.

If the screening survey is not completed online, study assessment staff will begin making recruitment calls to those who have not preemptively declined at least two calendar days after the recruitment packet is sent. If a potential participant did not receive the recruitment packet, upon request, we will email the recruitment packet to the individual. The consent and the recruitment flyer will also be available as downloadable PDF documents on the public access study recruitment website (no account needed). We will use IRB-approved email templates and will follow CHR guidelines in emails sent to potential participants regarding this study.

During the recruitment call, study staff will explain the study and answer questions. For those individuals who are interested, study staff will complete the screening survey. Individuals who pass the screening survey will be invited to complete the baseline survey after study staff obtains verbal informed consent as described in Section F.

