Demographics data will be collected on all potential participants during the screening process and/or baseline assessment and will include race, ethnicity, sex assigned at birth, gender identity, relationship status, employment status, and education and income information.

Survey Measures

All measures will be administered at the baseline assessment and all follow-up assessments unless otherwise indicated. The surveys will include questions from the following measures, either in part or in their entirety: **Patient Health Questionnaire-9 (PHQ-9); Seasonal Pattern Assessment Questionnaire (SPAQ); Quick Inventory of Depressive Symptomatology, self-report (QIDS-SR); Geriatric Depression Scale (GDS);** the abbreviated **self-report Columbia Suicide Severity Rating Scale (C-SSRS); Altman Self-Rating Mania Scale (ASRM); Generalized Anxiety Disorder-7 (GAD-7); Brief Medication Questionnaire (BMQ); Short Form 6 Dimension (SF-6D); Pittsburgh Sleep Quality Index (PSQI); Reduced Version of the Morningness-Eveningness Questionnaire (rMEQ); Split Week Self-Assessment of Sleep Survey (SASS-Y); Readiness Ruler (RR);**

Non-Standardized Measures to be collected include:

Alternative depression treatments. We will ask participants whether they are currently using, or intend to use, any “alternative” treatments for depression such as BLT (including whether light box purchase was new or had existing), yoga, Tai Chi, mood-enhancing diets (e.g., Mediterranean Diet), exercise, omega-3 fatty acids, St John’s wort, and others.

Satisfaction and Feedback. At the 2-month follow-up assessment, we will ask participants in Arms 2 and 3 about their experience as a participant in this study.

Actigraphy

Following the baseline and 2-month follow-up assessments, participants will be mailed an actigraphy device to wear for 10 days or until the battery dies and then return in supplied postage-paid envelope. We will download/score actigraphy data for sleep and physical activity using ActiLife software, then reset the actigraphy device and reuse it again with additional participants.

Ecological Momentary Assessment (EMA)

Up to 4 days per week during the 9-week acute intervention phase (baseline to 2-month follow-up), and twice weekly thereafter to 6 months, all participants will be sent text and/or email links to a brief EMA REDCap survey about mood and sleep in the last 24 hours. For participants in Arms 2 and 3, the EMA survey will also include brief questions about BLT adherence.

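### The EHR exclusion in section 5.b names bipolar I and II only, while section 9.a says the same search removes every recorded form; the two should be aligned

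*Protocol*

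**What the plan says.** The protocol states the scope of the bipolar exclusion in two places.

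- Section 5.b, EHR exclusion criteria: "EHR-recorded diagnoses of bipolar disorder I or II".
- Section 9.a, Risks to Subjects, under manic activation: "Our EHR case-finding program will exclude patients with any variation of bipolar disorder recorded in the EHR". The next sentence adds: "We will also screen for emerging symptoms of mania during the screening survey and follow-ups".

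The screening exclusions in 5.b add two relevant layers. One covers diagnoses and points back to the EHR list: "Contraindicated diagnoses or medications (see EHR exclusion criteria above) in case these are known to patients but are not EHR-recorded". A companion item for newly reported diagnoses points to the same list. The other covers symptoms: "Emergent bipolar, manic, mixed symptoms that may not have been formally diagnosed yet".

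Section 5.e lets the primary care provider or mental health specialist object before contact. Outreach goes ahead "unless we hear from the provider within three business days that it would be unwarranted".

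The SAP gives no eligibility criteria that would settle the difference.

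**The concern.** Section 5.b is where a reader looks to decide who may enter, and it is the natural source for the search specification. Section 9.a relies on that search as a protection against manic activation. If the rule in 5.b is narrower than the protection claimed in 9.a, the risk section promises more than the eligibility section delivers.

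The protocol gives this risk some prominence. Section 8 identifies triggering of bipolar disorder, in whatever form, as the likeliest anticipated event that could be related to the research. Light therapy is self-administered at home, and Arm 2 has no coaching contact.

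The scope of 5.b also matters after entry, because section 6 (Participant Withdrawal) lets the study team withdraw someone who develops a condition meeting the exclusion criteria.

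**Working it through.** No arithmetic applies to the inconsistency itself. The check is to take one patient through each stated entry rule.

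**Patient:** a recorded bipolar-spectrum diagnosis other than type I or II; a new unipolar or SAD diagnosis with a PHQ-9 of 10 or higher; no such depression diagnosis and no elevated PHQ-9 in the preceding 6 months; no bipolar, manic or mixed symptoms at screening.

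| Rule | Does it exclude this patient? |
|---|---|
| 5.b EHR inclusion (new unipolar or SAD code plus PHQ-9) | No. It does not require that a bipolar-spectrum code be absent. |
| 5.b EHR exclusion, chronic depression or earlier elevated PHQ-9 | No. The first concerns unipolar and SAD codes, the second a score. |
| 5.b EHR exclusion, contraindications | No. The conditions and drugs listed concern eye and skin phototoxicity. |
| 5.b EHR exclusion, bipolar | No. Types I and II only. |
| 5.b screening exclusions, contraindicated diagnoses | No. They refer back to the EHR list, so for bipolar disorder they reach types I and II at most. |
| 5.b screening exclusion, emergent symptoms | No, because this patient reports none. It would catch a patient with a recorded diagnosis who does report symptoms. |
| 5.e provider objection | Possibly. It is at the provider's discretion. |
| 9.a description of the EHR search | Yes. |

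Two further passages were checked.

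- *Screening survey, as described in 9.a.* For phototoxicity it covers diagnoses: "We will also ask about these diagnoses and conditions during the screening survey to further exclude those with these potential contraindications". For mania, 9.a mentions emerging symptoms only. As described, then, the survey does not fill the gap left by the I-or-II wording.
- *Baseline mania scale.* Section 6, Survey Measures, says: "All measures will be administered at the baseline assessment and all follow-up assessments unless otherwise indicated". That implies an Altman mania scale before randomisation, but no exclusion rule is tied to its score.

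**Result:** under 5.b alone the patient is not excluded; under 9.a the patient is. The other 5.b items do not clearly settle the matter.

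**The case against.** The strongest reply is that the two sentences are compatible. Section 9.a is itself a statement of what the program will do, and removing every form of bipolar disorder includes removing types I and II. Staff who follow both sentences exclude the patient. That is correct, and it limits the point: the gap appears only when 5.b is read alone. A reader might infer that no stated rule covers this patient, and the documents do not support that. The 9.a wording may also be loose shorthand for types I and II; in that case 9.a overstates the protection and the text still needs correcting.

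A reader might also infer that patients with bipolar-spectrum diagnoses are entering the trial. Nothing shows this. The case-finding code list and the screening survey are not in the documents, and either may already be broad. The patient described is narrow as well: no provider has objected, and none of the broadly worded screening symptoms is reported.

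Nor should the risk be inflated. Section 9.a calls it small and says that it exists in the general population whether or not a person enrols. Section 8 concerns what light therapy might trigger, not which earlier diagnoses raise the risk, and the documents do not say that other bipolar-spectrum codes carry a higher one. Further layers follow randomisation: the Altman scale at each follow-up, messages to usual-care providers of Arm 2 and 3 participants, and written information on recognising mania. These are real protections, but they do not decide who may enter.

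What stands is the mismatch between an operative eligibility rule and the safeguard attributed to it.

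**Conclusion.** The concern holds as an internal inconsistency in a safety eligibility rule. That the two texts differ in scope is certain; that the difference has any practical effect is not. The documents give no prevalence of other bipolar-spectrum codes in this population, so the number affected is unknown and may be zero. Power and the primary analysis do not depend on it.

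Little enrolment may remain to be affected. The protocol version is dated 13 September 2023, and section 6 estimates completion in May 2024.

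- If completion means the last 6-month assessment, enrolment ends in November 2023. That is 49 days (to 1 November) to 78 days (to 30 November) after this version, or about 1.6 to 2.6 months.
- If completion also covers a full 12 months of EHR follow-up, enrolment would have closed by May 2023, before this version.

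The main value of the correction is therefore likely to lie in the larger trial that this pilot prepares. Severity is minor: a low-cost safety alignment.

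**What to change.** 1. Change the bipolar item in the 5.b EHR exclusion criteria to any EHR-recorded bipolar-spectrum diagnosis: bipolar I, bipolar II, other specified, unspecified and cyclothymic. This brings 5.b into line with 9.a. Narrowing 9.a would also remove the conflict, but only by weakening a stated protection.
2. Confirm that the case-finding code list and the screening question on diagnoses match the new wording, and edit them only if they do not.
3. Carry the same wording into the future trial's protocol.
4. Optionally, count enrolled participants who have such a code. Section 6 describes EHR data on usual care, and the moderation analysis uses mental health comorbidities, but neither says that bipolar-spectrum codes are abstracted. A small additional query may be needed.

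The cost is one line of protocol text and a check of two existing tools. The downside is a slightly smaller recruitment pool.
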